## 6.4. COMMON CALCULATIONS

For quantitative measurements, change from baseline will be calculated as:

- Change from baseline = Test value at visit X – baseline value

## 6.5. SOFTWARE VERSION

All analyses will be conducted using SAS version 9.4 or higher.

## 7. STATISTICAL CONSIDERATIONS

### 7.1. MULTICENTER STUDIES

This study will be conducted by multiple investigators at multiple centers internationally. Data from all investigational centers will be pooled together in the primary/secondary analysis models.

Data from all investigational centers will also be pooled by region or country, depending of enrollment numbers, and will be used for subgroup analyses, if applicable.

### 7.2. MISSING DATA

Missing or partially missing concomitant medications and AEs start and stop dates will be imputed as described in [APPENDIX 2](#). However, imputed dates will NOT be presented in the listings as their sole

purpose will be for the classification of the medications as past, concomitant or post (refer to [section 9.5](#)) and the classification of the AEs as prior, treatment-emergent or post (refer to [section 9.9.1](#)).

Missing cataplexy attacks data will be handled as described in [sections 9.8.1.3](#) and [9.8.1.5](#).

Missing questionnaire data will be handled as described in the following sections:

- ESS:
  - Individual item scores: [section 9.8.2.1](#)
  - Total score: [section 9.8.2.2](#)
- PGIC and CGIc: [section 9.8.3.2.1](#)
- CGIs: [section 9.8.4.1](#)
- SF-36:
  - Scales and overall components: [section 9.8.3.2.2](#)
- EQ-5D-5L:
  - Dimensions: [section 9.8.3.1.4](#)
  - Crosswalk index score: [section 9.8.3.3.3](#)
- PHQ-9: [section 9.9.5.2](#)

Missing safety data (other than PHQ-9) will not be imputed.

### **7.3. ADJUSTMENTS FOR COVARIATE AND FACTOR TO BE INCLUDED IN ANALYSES**

The following covariate and factor will be included in the primary and secondary efficacy analyses. For details of their inclusion in the models, see the specific analysis section (i.e., [section 9.8.1.4](#)).

- Baseline value of efficacy endpoint of interest
- Pre-randomization Group
  - If there is less than 10 subjects in Group 1 (i.e. JZP-258 plus Placebo subjects) or less than 10 subjects in Group 2 (i.e. JZP-258 plus Placebo subjects), Groups 1 and 2 will be pooled together;
  - If there is less than 10 subjects in Group 3 (i.e. JZP-258 plus Placebo subjects) or Group 4 (i.e. JZP-258 plus Placebo subjects), Groups 3 and 4 will be pooled together;
  - If there is less than 10 subjects in pooled Groups 1 and 2 or pooled Groups 3 and 4, the stratification variable will be completely removed from the model.

## 7.4. MULTIPLE COMPARISONS/ MULTIPLICITY AND SIGNIFICANCE LEVELS

Subjects who are randomized to continue on JZP-258 in the DB RWP will be treated as a single group regardless of the dose of JZP-258 received. Thus, there will be no multiplicity issues with respect to multiple doses for hypotheses testing.

### 7.4.1. FINAL EFFICACY ANALYSIS AND TESTING PROCEDURE AT THE END OF MAIN STUDY

A hierarchical gate-keeping testing approach as described below will be used to test the primary and key secondary endpoints at the final efficacy analysis:

1. The primary endpoint will be tested first at a 2-sided significance level of 0.05;
2. If the primary endpoint reaches statistical significance, the key secondary endpoint will be tested at the 2-sided significance level of 0.05; otherwise the key secondary endpoint will not be tested.

All other secondary endpoints will be tested without multiplicity adjustments and nominal p-values will be provided.

Available safety data will also be summarized at the time of the final efficacy analysis. No statistical inferences are planned to be performed on any safety data.

### 7.4.2. FINAL SAFETY ANALYSIS AT THE END OF STUDY

A final safety analysis will be performed once all subjects have completed or terminated from the study. No statistical inferences are planned to be performed.

## 7.5. EXAMINATION OF SUBGROUPS

Subgroup analyses will be conducted on the primary and key secondary efficacy endpoints for the following:

- By Pre-randomization Groups;
- By gender;
- By region or country, depending of enrollment numbers

For the Pre-randomization Groups, if data are too sparse for at least one of the Pre-randomization Group, Groups might be pooled together in the subgroup analyses (refer to section 7.3) . Should there is less than 10 subjects in a pooled Pre-randomization group, then no subgroup analysis will be performed for that pooled Pre-randomization group. Summary statistics should still be presented for this subgroup, but no LS means, SEs, LS Mean Diff, 95% CI and p-value.

For the subgroup analyses by region or country, if data are too sparse for at least one country (i.e., less than 10 subjects), all European countries will be pooled together and all North American countries will be pooled together resulting in two regions: North American and Europe. Should there is less than 10 subjects in a region, then no subgroup analysis will be performed for that region. Summary statistics should still be

presented for this subgroup, but no LS means, SEs, LS Mean Diff, 95% CI and p-value.

It should be noted that the study was not designed to detect treatment differences with high statistical power within any subgroups.

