### **3.4. SAMPLE SIZE JUSTIFICATION**

Up to 185 subjects will be enrolled in the study to ensure a minimum of 130 subjects (65 subjects per treatment group) enter the DB RWP. This includes at least 50 subjects on Xyrem and 60 subjects using Xyrem plus other antiepileptics or non-Xyrem antiepileptic alone, as applicable.

A sample size of 65 subjects randomized per treatment group will provide at least 90% power to detect a difference in the change in mean weekly cataplexy attacks, from the OL SDP to the DB RWP, of 17.5 between JZP-258 and placebo. This assumes a common standard deviation (SD) of 30 and a two-sided significance level of 0.05 using a t-test. Assuming a 30% dropout rate prior to randomization, approximately 185 subjects will be enrolled to ensure that a minimum of 130 subjects enter the DB RWP. Assumptions were conservatively based on previous completed Xyrem studies GHB-2, OMC-SXB-15, and OMC-SXB-21 and account for study design. From these 3 studies, the mean weekly reduction in cataplexy attacks of Xyrem compared to placebo (common SD) ranged from approximately 10 (30) to 16 (28).

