#### **9.8.1.6. SUBGROUP ANALYSIS OF PRIMARY EFFICACY ENDPOINT**

Subgroup analyses for groups specified in [section 7.5](#) will be performed for the primary efficacy endpoint. These subgroups will be analyzed similarly to the primary efficacy analysis with the exception that for the Pre-randomization Group subgroup analyses, the Pre-randomization Group fixed effect will be excluded from the ANCOVA models.

A forest plot including each subgroup by randomized treatment group will also be provided.

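### The SAP reports a p-value within each subgroup but specifies no treatment-by-subgroup interaction, so no planned analysis directly assesses whether the effect differs between subgroups

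*SAP*

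**What the plan says.** SAP 7.5 plans subgroup analyses of the primary and key secondary endpoints by Pre-randomization Group, by gender, and by region or country. SAP 9.8.1.6 covers "Subgroup analyses for groups specified in" that section. It applies the primary analysis within each subgroup, leaves out the Pre-randomization Group term when that is the subgroup factor, and adds a forest plot. The primary analysis in SAP 9.8.1.4 ends in an LS mean difference, a 95% CI and a p-value for no treatment difference. If the rank branch is used, it ends in a rank-ANCOVA p-value with a Hodges-Lehmann shift and CI. SAP 9.8.2.5 does the same for ESS and adds stimulant use as a factor.

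The limit on inference is 10 subjects, both arms together. For a pooled Pre-randomization Group or a region below that size, "Summary statistics should still be presented for this subgroup, but no LS means, SEs, LS Mean Diff, 95% CI and p-value". No floor is stated for gender. Under SAP 7.3, Groups 1 and 2 (or 3 and 4) are pooled when one of the pair has fewer than 10 subjects.

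SAP 7.5 also cautions that "the study was not designed to detect treatment differences with high statistical power within any subgroups". It gives no rule for reading the separate p-values. Neither Protocol 9.13 nor the SAP text specifies a treatment-by-subgroup interaction term, estimate or test. SAP 8 refers to table and figure shells, which are not among the documents.

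**The concern.** A p-value within a subgroup asks whether the effect is detectable in that part of the sample, and the answer depends heavily on subgroup size. It does not ask whether the effect differs from that in the other subgroups.

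The second question matters here. Randomization is stratified by Pre-randomization Group. Groups 1 and 2 convert gram for gram from Xyrem, while Groups 3 and 4 start JZP-258 and titrate (Protocol 5.1.1.3). The two formulations were not bioequivalent when fasted (Protocol 1.4.1). A reader will want to know whether the effect is similar across prior treatments. If given a column of separate p-values, the reader may take one above 0.05 as evidence that the drug does not work in that group.

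**Working it through.** **Inputs (SAP 3.4).** "A sample size of 65 subjects randomized per treatment group will provide at least 90% power" for a difference "of 17.5 between JZP-258 and placebo". "This assumes a common standard deviation (SD) of 30", with "a two-sided significance level of 0.05 using a t-test". Allocation is 1:1, stratified by Pre-randomization Group (SAP 3.3). The documents do not give randomized group sizes, so every split below is an assumption.

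**Formula.** Power = P(|T| > t(0.975, n1+n2−2)), where T is noncentral t with noncentrality 17.5 / (30·√(1/n1+1/n2)).

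**The plan's own figure.** With 65 per arm the noncentrality is 17.5/(30·√(2/65)) = 17.5/5.262 = 3.33, and power is 0.910. This agrees with the stated 90% or more.

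**Power within a subgroup, same inputs**

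| Subjects, both arms | Power |
|---|---|
| 10 (5 per arm; noncentrality 0.92) | 0.129 |
| 21 | 0.245 |
| 32 (16 per arm; noncentrality 1.65) | 0.359 |
| 33 | 0.368 |
| 35 | 0.388 |
| 53 | 0.549 |
| 65 | 0.639 |

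**Chance that at least one subgroup has p>0.05 when the true effect is uniform.** The groups are disjoint, so this is 1 minus the product of the powers.

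- Four equal groups (32/33/32/33): 1 − 0.359² × 0.368² = 0.983.
- Enrolment targets scaled to 130: 50/185 × 130 ≈ 35; 60/185 × 130 ≈ 42, split 21/21; remainder 53. 1 − 0.388 × 0.245 × 0.245 × 0.549 = 0.987.
- One group at 10 (35/10/32/53): 0.990.
- A search over four-way splits with at least 10 per group, in steps of 2, found no value below 0.983.
- Two sexes, 65 each: 1 − 0.639² = 0.592.

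**How the 98% moves**

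- Pooling under SAP 7.3: about 90% or more with three groups. With two groups it runs from 59% (65/65) to 89% (120/10).
- Smaller residual SD after covariate adjustment (assumed values; four equal groups): 94% at SD 25, 79% at SD 20, 36% at SD 15. The documents give no adjusted SD.
- Effect and SD from the earlier Xyrem studies in SAP 3.4 (four equal groups): 98.5% for 16 (28) and 99.9% for 10 (30).

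**Chance of a zero or wrong-sign estimate in at least one group (17.5, SD 30).** For 32 subjects the chance is Φ(−1.65) = 0.049, and for 33 it is 0.047. Across four equal groups, 1 − 0.951² × 0.953² ≈ 0.18. With one group at 10 it is 0.26.

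**What an interaction model would and would not change**

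- With one model, four equal groups and pooled error on 130 − 8 = 122 df, power per group is 37–38%. At least one subgroup CI still includes zero about 98% of the time.
- Interaction test, one of four groups truly at zero and the others at 17.5: the mean effect is 13.125. The squared deviations sum to 3 × 4.375² + 13.125² = 229.7. The noncentrality is 229.7 × 32.5/(4 × 900) = 2.07 on 3 and 122 df, and power is about 19%.
- Interaction test by sex, 17.5 against zero: SE = 30·√(4/32.5) = 10.5, noncentrality 1.66, power about 38%.

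**The case against.** The strongest reply is that the planned display already serves the purpose. The forest plot and subgroup CIs show consistency descriptively, and under a uniform effect most estimates will point the same way. The SAP warns that subgroup power is not high. SAP 7.4.1 confines confirmatory testing to the primary and key secondary endpoints, so no Type I error is at stake. All of that stands. A reader might infer from the 98% that the drug would look ineffective or reversed in some group. The documents do not support that: p>0.05 is not a null estimate, and a zero or wrong-sign estimate in at least one group has a chance of about 18–26%. Nor does the SAP say that subgroup power is absent; it says only that the study was not designed for high power there.

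It is also fair that the remedy is modest. Subgroup CIs from a common model would still often cross zero, and the interaction test is weak. The gain is a direct estimate of how much the effect differs, with its uncertainty, which separate models do not provide.

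The 10-subject case is an edge. At country level, one country below 10 leads to pooling into two regions. The EQ-5D-5L mapping in SAP 9.8.3.1.4 lists 17 enrolling countries, and 130/17 is under 8, so at least one country must fall below 10 if 130 are randomized.

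An interaction test shown only in the unavailable shells cannot be ruled out. The statement here is therefore limited to the SAP text.

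**Conclusion.** The point holds as a minor one. The SAP text reports separate treatment p-values by subgroup and specifies no analysis that directly assesses whether the effect differs between them.

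The size, about 36% power per group and about a 98% chance of at least one p>0.05, is for the primary endpoint. It rests on four unpooled groups, an assumed equal split, a uniform effect of 17.5, SD 30 and an unadjusted t-test. Of these, the split matters little, while pooling and residual SD matter a good deal. The planned ANCOVA or rank ANCOVA could have higher power than the t-test. The issue is interpretation of the subgroup output; the primary and key secondary conclusions do not change.

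**What to change.** In SAP 7.5, 9.8.1.6 and 9.8.2.5, fit one model per subgroup factor on the Efficacy Population. Include treatment, subgroup, treatment-by-subgroup, baseline and Pre-randomization Group (entered once when it is itself the factor). Show the subgroup estimates with 95% CIs on the forest plot, and report the interaction estimate with its CI and p-value. Drop the within-subgroup p-values or label them descriptive. State that the interaction test has low power, so a non-significant result does not prove consistency.

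The cost is SAP wording, minor programming and the loss of nominal subgroup p-values. No new data or design change is needed.

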## 8. OUTPUT PRESENTATIONS

APPENDIX 1 shows conventions for presentation of data in outputs.

The table, figure, and listing (TFL) shells provided with this SAP describe the presentations for this study and therefore, the format and content of the summary TFLs to be provided by [REDACTED] [REDACTED].

## 9. ANALYSES AT THE END OF THE MAIN STUDY

Final efficacy analyses and analysis of available safety data at the end of Main Study will include all the analyses described in the below sections where summaries will be presented by study period (OTTP, SDP, RWP, OLE) and across all study periods, as appropriate.

### 9.1. DISPOSITION AND WITHDRAWALS

All subjects who provide informed consent will be accounted for in this study.

[figure not shown]
The number of screened subjects will be presented overall. The number and percentages of screened failure subjects as well as enrolled subjects will be presented based on the SCR. For each period, the number and percentages of subjects who entered, received at least one dose, completed, are still ongoing and withdrew from each period, including reasons for withdrawal, will be presented overall and by Pre-randomization Group based on the ENR. The number of OLE reentry subjects, number of OLE roll-over subjects and number of subjects not entering OLE will be presented for the overall population and by pre-randomization group.

The number and percentages of subjects who received at least one dose, completed, are still ongoing and withdrew from the DB RWP, including reasons for withdrawal, will be presented overall and by randomized treatment group based on the RND.

Major protocol deviations as classified in the clinical trial management system (CTMS) will be summarized by category as defined in CTMS and presented overall and by Pre-randomization Group based on the ENR across all study periods.

All protocol deviations will also be provided in a listing.

The number and percentages of subjects included in and excluded from each analysis population as well as the reasons for exclusion from each analysis population will be summarized overall and by Pre-randomization group based on the ENR. A similar summary will be presented overall and by randomized treatment group based on the RND.

## 9.2. DEMOGRAPHIC AND OTHER BASELINE CHARACTERISTICS

Demographic and other baseline characteristics data will be summarized using descriptive statistics for the SAF and EFF.

Demographic and other baseline characteristics include:

- Age (years) when age can be derived, it will be calculated relative to date of signed informed consent; otherwise, the age entered by the sites will be used
- Birth gender
- Race - subjects who reported more than one race will be reported under 'multiple' race category
- Ethnicity
- Weight (kg)
- Height (cm)
- BMI (kg/m^2)
- Childbearing potential
- Pre-randomization group
- The Planned Dosing Information at randomization will be presented in the demographic and other baseline characteristic table for the EFF population.
  - Unequal Nighttime JZP-258 Dosages
  - Equal Nighttime JZP-258 Dosages
  - Twice Nightly JZP-258
  - Thrice Nightly JZP-258
- Region

### 9.2.1. DERIVATIONS

- Age (years)= largest integer less than or equal to [(date of informed consent – date of birth) + 1] / 365.25
- BMI (kg/ m^2) = weight (kg)/ height (m)

## 9.3. SURGICAL AND MEDICAL HISTORY

Surgical and medical history will be coded using the Medical Dictionary for Regulatory Activities (MedDRA) dictionary, version 19.1, and are defined as those medical conditions/ diseases which stopped prior to or on the date of Main Study informed consent form (ICF) signing.

The following summaries will be provided for the surgical and medical history data based on the SAF and EFF.

- Past surgeries and medical conditions/diseases, other than narcolepsy/cataplexy by System Organ Class (SOC) and Preferred Term (PT)

If a subject reports a past medical condition/disease, surgery or past medication more than once within a SOC or PT, the medical condition/disease, surgery or past medication will be reported only once for that SOC or PT.

For OLE re-entry subjects, surgical and medical history that started after a subject completed the Main Study Safety Follow-up visit and stopped before OLE Day 1 will not be summarized. Such medical conditions/ diseases will be included in subject data listings only.

Disease history, such as cataplexy, will be summarized for the SAF and EFF. Disease history variables include:

- Time since diagnosis of narcolepsy (years) - calculated relative to date of the signature of the ICF
- Symptoms of narcolepsy (current and past, including symptoms experienced prior to any narcolepsy treatment)

### 9.3.1. DERIVATIONS

- Time since symptoms onset (years)= [(date of the signature of the ICF – date of symptoms onset + 1) / 365.25]
- Time since diagnosis (years)= [(date of the signature of the ICF – date of diagnosis) + 1] / 365.25

## 9.4. CONCURRENT CONDITIONS/ DISEASES

Concurrent medical conditions/diseases will be coded using the MedDRA dictionary, version 19.1, and are defined as those medical conditions/ diseases which started prior to or at the Screening visit of the Main Study that are still ongoing as of the date of the Main Study ICF signature.

The following summary will be provided for the concurrent conditions/diseases data based on the SAF and EFF.

- Concurrent medical conditions/diseases, other than narcolepsy/cataplexy by SOC and PT

For OLE re-entry subjects, concurrent conditions/diseases which started after the completion of the Main Study Safety Follow-up visit and that stopped before OLE Day 1 will not be summarized. Such concurrent conditions/ diseases will be included in subject data listings only.

## 9.5. PAST, CONCOMITANT, AND POST MEDICATIONS

Medications will be coded to the anatomical therapeutic class (ATC) level 4 and preferred drug name using the World Health Organization (WHO) drug dictionary, version 01Sep2016E, and will be classified as

follows:

- **Past medications** are defined as any medications which started prior to the first dose of OL study drug in the OTTP.
- **Concomitant medications** will be defined as any medications started prior to, on or after the first dose of OL study drug up to the last dose of study drug during the OTTP, SDP, RWP or OLE period (whichever is the latest) which ended on or after the first dose of OL study drug. Concomitant medications will be also defined for each study period as follows:
  - **For the OL Optimized Treatment and Titration Period**, concomitant medications are defined as any medications that ended on or after the first dose of OL study drug in the Optimized Treatment and Titration Period and started prior to, on or after the first dose of OL study drug in this study period up to
    - the end of treatment in this study period for subjects who entered the OL Stable-Dose Period
    - the last dose of OL study drug in the OL Optimized Treatment and Titration Period for subjects who discontinued early in the OL Optimized Treatment and Titration Period;
  - **For the OL Stable-Dose Period**, concomitant medications are defined as any medications that ended on or after the first dose of OL study drug in the OL Stable-Dose Period and started prior to, on or after the first dose of OL study drug in this study period up to
    - the end of treatment in this study period for subjects who entered the DB Randomized-Withdrawal Period
    - the last dose of OL study drug in the OL Stable-Dose Period for subjects who discontinued early in the OL Stable-Dose Period;
  - **For the DB Randomized-Withdrawal Period**, concomitant medications are defined as any medications that ended on or after the first dose of DB study drug in the DB Randomized-Withdrawal Period and started prior to, on or after the first dose of DB study drug up to
    - the end of treatment in this study period for subjects who entered the OL Extension Period
    - the last dose of DB study drug in the DB Randomized-Withdrawal Period for subjects who discontinued early in the DB Randomized-Withdrawal Period;
  - **For the OL Extension Period**, concomitant medications are defined as any medications that ended on or after the first dose of OL study drug in the Open Label Extension Period and started prior to, on or after the first dose of OL study drug in this study period up to the last dose of OL study drug in the OL Extension Period;
- **Post medications** are defined as any medications that started after the last dose of study drug during the OTTP, SDP, RWP or OLE period (whichever is the latest).

Medications that span across periods will be counted as concomitant medications for each of the periods where the definition is met. For OLE re-entry subjects, medications which started after the completion of the Main Study Safety Follow-up visit and stopped before OLE Day 1 will be classified as post medications

only. Medications which started after the completion of the Main Study Safety Follow-up visit and were ongoing on OLE Day 1 will be classified as concomitant and post medications.

See APPENDIX 2 for handling of partial dates for medications.

The number of subjects with at least one past medication for the following specific indications will be summarized for the SAF and EFF: cardiovascular, pulmonary, gastrointestinal, hepatic, renal, immunologic, neurologic and psychiatric diseases.

In addition, the number of subjects for the following Xyrem dosing information at study entry groups will be summarized for the SAF and EFF.

- Unequal Nighttime Xyrem Dosages
- Equal Nighttime Xyrem Dosages
- Twice Nightly Xyrem
- Thrice Nightly Xyrem

Disease-related medications will be defined as those medications taken for the treatment of narcolepsy and its symptoms (i.e., medications that have been indicated as either for the “treatment of narcolepsy and its symptoms” or “antecataplectic” in the CRF). Other medications will be defined as all medications other than disease-related medications.

Disease-related concomitant medications and other concomitant medications will be summarized by ATC level 4 and preferred drug name overall and by Pre-randomization Group for each period based on the corresponding period SAF population. For the DB RWP, the summary will be provided by ATC level 4 and preferred drug name by randomized treatment group.

The average time to taper off antiepileptic medication will be summarized for Pre-randomization Group 2 and Group 3 subjects combined. For each subject, Time to taper off antiepileptic medication, in days, is the time from the Study Day 1 to one day after the latest end date of the concomitant medication taken as an antiepileptic during the TTP. Antiepileptic medications discontinued prior to Study Day 1 were not included in the summary of time to taper off.

Another table will summarize the number and percentage of subjects on stimulant use during SD and DB RWP periods. The list of stimulant medication will be provided by Jazz.

Past and post medications will be provided in subject data listings only.

